## **7.5 Study Population**

A total of 360 subjects who meet the following criteria will be enrolled and determined eligible in this study:

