## 11.0 STATISTICAL METHODS

This is a prospective, multicenter study with a randomized, controlled sub-study that is designed to evaluate the safety and effectiveness of the scleral implant procedure. The percentage of primary eyes achieving the effectiveness endpoint will be evaluated at 12 months postoperatively. Within the study cohort, a subgroup will be randomized on a 1:1 ratio to a surgery group and a control group. Subjects in the randomized control group will not receive surgery and will be examined at 3 months and 6 months. After completion of the 6 month observation period, subjects in the randomized control group will be eligible to receive surgery as part of the 360 subject cohort. This randomized controlled sub-study will be used to evaluate the effectiveness of the scleral implant procedure in the randomized surgery group compared to effectiveness in the randomized control group at 6 months postoperatively.

The effectiveness endpoint, hypotheses, sample size calculations, analysis population, handling of missing data, analysis methods, and analysis of safety data are as follows.

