#### Full Study Cohort Effectiveness Endpoint

The sample size calculation for the statistical hypotheses described for Objective #1 in Section 11.2 is based on the following criteria:

- The two-sided significance level = 0.05 (or one-sided significance level = 0.025).
- The statistical power = 90% at  $p = 0.825$ . The assumption of true responder rate of 0.825 is based on the simple average of success rate observed in previous Refocus clinical study data, as follows:
  - Disposable Scleratome group had an observed success rate of 88%.
  - Re-usable Scleratome group had an observed success rate of 77%.
  - Simple average of 88% and 77% is 82.5%.
- Binomial distribution is used for sample size calculation.

Based on the criteria above for Objective #1, 330 treated primary eyes should be available for analysis at 12 months. If a dropout rate of 10% of subjects by 12 months is considered, then the surgery cohort should include approximately 360 treated primary eyes.

For safety analysis, in order to detect an Adverse Event (AE) with a true probability of occurrence among subjects of 1% with 95% probability, based on the binomial distribution, a sample of at least 299 eyes would be required (in accordance with ANSI Z80 29 18Nov2013 AIOL [rev20]). Assuming a drop-out rate of approximately 10% of subjects by 12 months, the surgery cohort should include a minimum of 333 treated primary eyes.

A sample size of 333 treated primary eyes will meet the sample size requirements for both safety and effectiveness. The study cohort is planned for 360 surgery subjects at up to 14 study sites. However, no site may enroll and determine to be eligible more than 20% of the subject surgery cohort.

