## 11.6 Analysis of Effectiveness Cohorts

For the primary analysis of Objective #1, all observed 12-month data of the surgical primary eyes will be included in the effectiveness analysis. Missing data will not be imputed except that explanted primary eyes will be imputed as failures.

For the primary analysis of Objective #2, all reported 6-month data of the randomized primary eyes will be included in the analysis. Missing data will be imputed as follows:

- Randomized Control Group: In the absence of 6 month visit data, the nearest available data recorded between and including the 3 month visit up to the 6 month visit will be utilized. Since this randomized control group does not receive the benefit of the surgery during this 6 month observation period, the lost to follow-up and missed visit rate could be higher and since no intervention occurs during the 6 month period, this imputation of missing data is warranted. In the absence of any observed data between the 3 month visit

and 6 month visit, this missing data will not be imputed since failure to achieve the effectiveness endpoint is expected.

- Randomized Surgery Group:
  - Explanted primary eyes will be imputed as failures.
  - In the absence of 6 month visit data, the nearest recorded data after 6 months up to and including 12-month visit data will be used. This imputation is warranted as the visit data between 6 and 12 months provides a predictive indicator of 6 month results. In the absence of any observed data between 6 and including 12 months, this other missing data will not be imputed.

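### Section 11.3 says 333 treated eyes satisfy both safety and effectiveness, but 333 is the safety figure only; at the plan's 10% dropout it leaves about 300 evaluable eyes against the 330 required for Objective #1.

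*Combined protocol and SAP*

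**What the plan says.** Section 11.3, under Full Study Cohort Effectiveness Endpoint, gives two sample-size derivations at the same dropout allowance.

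- **Effectiveness (Objective #1).** One-sided alpha 0.025, 90% power at a true 12-month responder rate of 0.825 against the 75% goal, exact binomial. The result is that "330 treated primary eyes should be available for analysis at 12 months". Allowing 10% dropout, "then the surgery cohort should include approximately 360 treated primary eyes".
- **Safety.** To see at least one event of 1% true frequency with 95% probability, 299 eyes are needed. Allowing about 10% dropout, "the surgery cohort should include a minimum of 333 treated primary eyes".

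The subsection then concludes: "A sample size of 333 treated primary eyes will meet the sample size requirements for both safety and effectiveness". The sentence after it reads: "The study cohort is planned for 360 surgery subjects at up to 14 study sites".

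For the Objective #1 analysis, Section 11.6 says: "Missing data will not be imputed except that explanted primary eyes will be imputed as failures".

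**The concern.** When two requirements apply to one cohort, the larger must govern. Here the larger is about 360 treated eyes, for effectiveness, yet the concluding sentence names the smaller, the safety minimum. Under Section 11.6, an eye with no 12-month data drops out of the Objective #1 denominator unless it was explanted, so dropout directly reduces the number analysed.

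Objective #1 is one of two tests that must both succeed (Sections 11.3 and 11.8). A reader who relied on this sentence would accept 333 treated eyes as enough for 90% power on it, which the plan's own figures do not support.

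**Working it through.** **Inputs.** From Section 11.3: one-sided alpha 0.025, true rate 0.825, 90% power, 330 evaluable eyes, 10% dropout, 299 eyes for safety. From Section 11.8: the goal is met if the exact one-sided 97.5% lower limit is at least 75%. From Section 11.6: missing 12-month data are not imputed, except that explants count as failures.

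**Step 1. Reproduce the plan's effectiveness figure.** For n evaluable eyes, let r be the smallest responder count whose exact one-sided 97.5% lower limit is at least 0.75. Power is P(X ≥ r) with X ~ Binomial(n, 0.825).

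- n = 330: r = 264, power 89.6%. This agrees with the stated 90% to within rounding.
- The continuity-corrected normal formula gives n = 330.3, which also matches.
- Inflation: 330/0.9 = 366.7, or 330 × 1.1 = 363. The plan's approximate 360 is close to both.

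**Step 2. Reproduce the plan's safety figure.** 1 − 0.99^298 = 94.996% and 1 − 0.99^299 = 95.05%, so 299 is the smallest sufficient number. 299/0.9 = 332.2, rounded up to 333. So 333 is the safety number after inflation for dropout.

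**Step 3. Apply the plan's dropout to 333 treated eyes.**

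- Evaluable: 333 × 0.9 = 299.7. That meets 299 within rounding and is about 30 below 330.
- Dropout at which 333 treated would still leave 330: 1 − 330/333 = 0.9%, or 3 eyes.
- If each eye drops out independently with probability 10%, the chance of at least 330 evaluable from 333 treated is below 0.01%.

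**Step 4. Power at the resulting numbers.** At fixed evaluable counts:

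| Evaluable n | Critical count r | Exact power at 0.825 |
|---|---|---|
| 299 | 240 | 86.2% |
| 300 | 240 | 88.7% |
| 318 (smallest n reaching 90%) | 254 | 90.2% |
| 324 | 259 | 89.9% |
| 330 | 264 | 89.6% |

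The exact power curve is saw-toothed, so a single n can mislead. Averaging over evaluable counts distributed Binomial(treated, 0.9) smooths it:

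| Treated eyes | Expected evaluable | Averaged power |
|---|---|---|
| 330 | 297 | 87.0% |
| 333 | 299.7 | 87.3% |
| 360 | 324 | 89.9% |
| 367 | 330.3 | 90.4% |

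The planned 360 treated eyes deliver the design intent; 333 do not.

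**Step 5. What 360 counts.** Section 11.3 treats 360 as surgery subjects and treated primary eyes. Section 7.5 says: "A total of 360 subjects who meet the following criteria will be enrolled and determined eligible in this study". Section 11.0 says that after six months "subjects in the randomized control group will be eligible to receive surgery as part of the 360 subject cohort", and Section 7.2 exits controls who decline. The sub-study has 30 controls, and no election rate is given. Purely as an assumption range, before any other surgical withdrawals, treated eyes run from 360 − 30 = 330 (no control elects surgery) to 360 (all do), and averaged power runs from 87.0% to 89.9%.

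**The case against.** The strongest reply is that the sentence decides nothing. The next sentence plans 360, the synopsis and Sections 7.2 and 7.5 also give 360, and no rule stops enrolment at 333. This stands, and it is why the point concerns the accuracy of the justification rather than an underpowered trial.

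A second reply is that 333 may have been meant as eyes analysed. Section 11.3 does use the word treated for the 330 eyes available at 12 months, and 333 analysed eyes would meet both requirements with 90.7% power. This does not hold, because the immediately preceding sentence derives 333 as the cohort to be treated so that about 299 remain after dropout.

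Third, the shortfall is small: about 87% to 89% power instead of 90%, with 2.5 points of movement between 299 and 300 eyes coming from discreteness alone. That is correct, and the averaged 87.3% is the fairer single figure.

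Fourth, explanted eyes stay in the denominator as failures, and the plan does not say whether its 10% dropout includes them. If it does, somewhat more than 300 eyes would be analysed. This is a fair qualification, but it does not make 333 treated eyes satisfy the plan's own requirement of about 360.

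Finally, the meaning of 360 is a separate question from the 333 sentence. Agreed; it is raised here only as a clarification, and the conclusion does not depend on it.

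**Conclusion.** The concern holds. Both derivations in Section 11.3 reproduce; the sentence combining them does not. At the plan's 10% dropout, 333 treated eyes give about 300 evaluable for Objective #1, not 330, and averaged power of 87.3% rather than 90%. This assumes that dropouts are lost from the denominator and that the true responder rate is 0.825, both as the plan has it.

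The planned 360 treated eyes, if all are treated, give about 324 evaluable and 89.9% power, so the trial as planned is not underpowered by this error. It should be corrected because it is a false statement of sufficiency about the sample size for a test that must succeed.

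**What to change.** In Section 11.3, limit the 333 sentence to safety. For example: 333 treated primary eyes meet the safety requirement; the effectiveness requirement rests on 360 treated primary eyes, which at 10% dropout give about 324 evaluable eyes and exact power of about 90%. If exactly 330 evaluable eyes are intended, note that this corresponds to 367 treated (330/0.9 = 366.7).

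As a separate clarification, state whether 360 means treated primary eyes or eligible subjects including the 30 controls, and use that definition consistently in the synopsis and Sections 7.2, 7.5, 11.0 and 11.3.

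The cost is one reworded sentence and one definition. Correcting the 333 sentence requires no added enrolment. If 360 is defined as treated eyes, the count of eligible subjects in Section 7.5 will supply that number only if every control elects surgery and nobody withdraws before it, so the sponsor should check the two figures against each other.

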#### Randomized Sub-study

The sample size for Objective #2 in Section 11.2 is based on the following criteria:

- The two-sided significance level = 0.05 (or one-sided significance level = 0.025).

- Based on the randomized control group data collected in IDE G970152, the 6-month responder rate is estimated as 10% for the control group.
- Based on the surgery group data collected in IDE G970152, the 6-month responder rate was lower than the 12-month responder rate. Therefore, it is assumed that the 6-month responder rate of the randomized surgery group in this study will be approximately 0.75.
- The statistical power = 90%.
- Fisher's exact test is used for sample size calculation.

Based on the criteria above, a sample of 14 randomized surgery group primary eyes and 14 randomized control group primary eyes at 6 months will ensure a power greater than 90% for Objective #2, using a one-sided alpha of 0.025.

A sample size of 30 randomized surgery group subjects and 30 randomized control group subjects has been selected which will account for a possible 10% subject drop-out rate and allow for greater accuracy in point estimates for both groups. This randomized sub-study will be conducted at 3 clinical sites. Sites will be chosen based on availability of equipment for additional sub-study measures, such as availability of an iTrace unit (Tracey Technologies, Houston, TX), and the ability and willingness of the site to participate in the additional sub-study. The target enrollment at each of the 3 sites in the randomized sub-study will be 20 eligible subjects to provide an even distribution. However, no site may enroll and determine eligible more than half of the randomized sub-study cohort or 30 subjects.

[figure not shown]
#### **11.4 Cohort Population**

Potential subjects will sign a screening consent to undergo preliminary screening for eligibility that consists of standard of care eye examinations. Subjects who may be eligible based on the preliminary screening criteria and are willing to participate in the study will sign a full informed consent and are considered enrolled. At that time, the study specific examinations required to complete the baseline examination will be administered to determine eligibility for the study. Subjects who have signed the full informed consent but do not meet all of the inclusion and exclusion criteria will be considered enrolled but ineligible for the study. The reason for the disqualification will be recorded and reported.

**Safety Cohort:** All eyes (both primary and fellow eyes) that have undergone surgical preparation of the ocular surface.

**Effectiveness Cohort:** All primary eyes that have been implanted with at least one implant segment and primary eyes of subjects that have been enrolled and determined eligible in the randomized control group.

Figure 9, below, summarizes the status of enrolled subjects and the cohort populations for the study, except that the randomized control group is not shown.

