## **8.0 STUDY METHODS**

### **8.1 Patient Screening and Enrollment**

Prior to enrollment in the study, interested subjects will be screened to determine initial eligibility. The investigator or a designee will explain the study purpose and summary procedures and subject responsibilities to the potential subject. If it appears that the subject is interested and may be a candidate for the study, the subject will be asked to review and sign a Screening Informed Consent. The Screening Informed Consent provides a summary of the preliminary screening testing which will include standard of care testing including a medical history, vision testing and an examination of ocular health.

If preliminary eligibility is met, the subject will be asked to sign a Study Informed Consent Form which describes the surgical procedure; the potential benefits and risks, study examinations to be conducted, the frequency of follow-up visits, the expense reimbursement to be provided to the subject as well as other topics. When the Study Informed Consent is signed by the subject and by the Investigator or designee, the Subject is considered to be enrolled. Additional study specific testing of the subject's ocular and medical condition as specified in the baseline examination will be performed to determine eligibility. If during this testing, the Investigator or Sub-Investigator determines that the subject will not meet the protocol inclusion or exclusion criteria the examination may be terminated.

If the subject satisfies all inclusion and exclusion criteria, the full baseline examination data will be provided to the Sponsor for verification that all data have been obtained and meets eligibility criteria. Upon approval by the Sponsor, the subject will be scheduled for surgery if the subject has been enrolled and determined to be eligible at an Investigational site that is participating in the non-randomized cohort.

If the subject has been enrolled and determined to be eligible at an Investigational site that is participating in the randomized controlled sub-study, the subject will be randomized (1:1 ratio) to either the surgery group or the control group. Subjects randomized to the control group will be followed for 6 months, and will be eligible to undergo VisAbility Implant surgery after completion of the six month observation period.

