## 8.5 Scheduled Post-Operative Visit Schedule

### 8.5.1 Primary Eye Visit Schedule

Subjects enrolled and eligible in the non-randomized cohort of the study and subjects enrolled, eligible and assigned to the randomized surgery group will be examined according to the following schedule based on the date of primary eye surgery. Surgery on the primary eye may not occur more than 60 days after a baseline examination establishing eligibility. Visit windows are calculated on a 30 day month.

Pre-operative Baseline Evaluation	(Day -60 to Day -1)
Surgery	(Day 0)
One Day Exam	(18 to 36 hours)
One Week Exam	(7 days +/- 2 days)
One Month Exam	(1 month +/- 7 days)
Two Month Exam	(2 months +/- 14 days)
Three Month Exam	(3 months +/- 14 days)
Six Month Exam	(6 months +/- 21 days)
Twelve Month Exam	(12 months +/- 45 days)
Eighteen Month Exam	(18 months +/- 45 days)
Twenty-four Month Exam	(24 months +/- 60 days)

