#### Objective #2:

An analysis of the randomized surgery group and randomized control group will be conducted. The randomized surgery group is defined as successful if the percentage of primary eyes achieving the effectiveness endpoint at 6 months postoperative (6-month responder rate) is higher than the percentage in the randomized control group. The corresponding null and alternative hypotheses are as follows:

$H_0$  (null hypothesis):  $p_1 \leq p_2$

$H_a$  (alternative hypothesis):  $p_1 > p_2$

Where:

- $p_1$  is the percentage of primary eyes in the randomized surgery group who achieve the effectiveness endpoint at 6 months.
- $p_2$  is the percentage of primary eyes in the randomized control group who achieve the effectiveness endpoint at 6 months.

The primary eye is defined as the subject's dominant eye and the eye that will undergo surgery first. It is intended that all subjects will also undergo surgery in the fellow eye at a subsequent date as specified in the protocol.

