**FIGURE 9 – ILLUSTRATION OF STUDY POPULATION AND ACCOUNTABILITY**

## 11.5 Subject Accountability

The following terms and definitions will be used for the accountability of the study population and are based on the definitions found in ANSI Z80.29 Rev 018, section B.5.3 as modified and explained below.

- Enrolled – the total number of subjects that have signed the full informed consent.
  - Enrolled but ineligible – the total number of subjects that have signed the full informed consent but do NOT meet all of the inclusion/exclusion criteria.
  - Enrolled and eligible – the total number of subjects that have signed the full informed consent and meet all of the inclusion/exclusion criteria.
- Surgical Withdrawal – Subjects (eyes) that have been enrolled and determined eligible but do not undergo surgical preparation of the ocular surface for any reason.
- Discontinued– Subjects (eyes) that have discontinued treatment prior to the visit window associated with the form as a result of death, the removal of all 4 implant segments (explant), or any other reason except lost to follow-up.
  - Explanted Eye – Eyes that underwent implantation surgery, but have had all implanted segments removed.
- Lost to Follow-up – Subjects that have withdrawn from the study after initial eye surgery or subjects that have missed the visit window associated with the form and all subsequent scheduled visits despite documented efforts by the Investigator to schedule the subject for follow-up.
- Missed Visit – Data for subjects (primary eyes) that is not available for a follow-up visit within the specified visit window associated with the form, but data is available for a subsequent follow-up visit for such subject.

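### The Objective #2 cohort takes surgery eyes by implantation but control eyes by assignment, so subjects randomized to surgery and never implanted leave the only randomized comparison

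*Combined protocol and SAP*

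**What the plan says.** - Section 8.1: once eligibility is confirmed at a sub-study site, "the subject will be randomized (1:1 ratio) to either the surgery group or the control group". Randomization thus comes before surgery, which Section 8.5.1 allows up to 60 days after the baseline examination.
- Section 8.5.1: surgery-group subjects "will be examined according to the following schedule based on the date of primary eye surgery". Section 8.5.2 starts the control clock at randomization.
- Section 11.2, Objective #2: p1 "is the percentage of primary eyes in the randomized surgery group who achieve the effectiveness endpoint at 6 months". Section 11.8 applies Fisher's exact test to the two randomized groups.
- Section 11.4: the Effectiveness Cohort is "All primary eyes that have been implanted with at least one implant segment and primary eyes of subjects that have been enrolled" and judged eligible in the control group.
- Section 11.5: Surgical Withdrawal covers eligible subjects or eyes "but do not undergo surgical preparation of the ocular surface for any reason". It is listed apart from Discontinued. An explanted eye must first have had implantation surgery.
- Section 11.6: for Objective #2, "all reported 6-month data of the randomized primary eyes will be included in the analysis". Explanted surgery eyes count as failures, and a missing 6-month value may be borrowed from later data up to month 12. For the rest, "In the absence of any observed data between 6 and including 12 months, this other missing data will not be imputed". For controls with nothing from month 3 to month 6, "this missing data will not be imputed since failure to achieve the effectiveness endpoint is expected".
- Section 11.8, sensitivity analysis of Objective #2: discontinued eyes are imputed in every combination, and each result is compared with a 75% lower confidence limit.

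**The concern.** The hypothesis is stated for groups formed by randomization, but the analysis cohort applies a condition met after randomization, and in one arm only. Subjects assigned to surgery who withdraw beforehand, or whose eye is prepared but receives no segment, are outside the cohort. An eligible control stays in the cohort by assignment alone.

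This is the trial's only randomized comparison. Section 11.3 finds 14 eyes per arm sufficient for power and takes 30, partly to obtain more accurate point estimates. Leaving out subjects who could not have benefited from the implant moves the surgery estimate, and the difference from control, in the device's favour.

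**Working it through.** **Following a never-implanted subject through the plan.**
1. Not in the Effectiveness Cohort, because no segment was implanted (11.4).
2. Suppose the randomized primary eyes of 11.6 are read generously as all randomized eyes. The subject still has no 6- or 12-month visit, because the surgery-arm clock starts at surgery (8.5.1).
3. Not imputed as a failure, because only explanted eyes are and those must first have been implanted (11.5, 11.6).
4. Other missing data are left unimputed (11.6), so the subject is in neither numerator nor denominator.
5. Not named in the tipping-point analysis, which varies discontinued eyes; Surgical Withdrawal is a separate category (11.5).

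Deleting the implantation condition from 11.4 would therefore not be enough by itself.

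**Inputs (11.3).** 30 per arm; control rate 10%; surgery rate 0.75; two-sided 0.05; Fisher's exact test. The plan gives 0.75 for the randomized surgery group; applying it to implanted eyes is an assumption made here. The number never implanted, k, is also an assumption.

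**The plan's own figure.** Exact enumeration at 14 per arm, 75% against 10%, gives 93.4% power, so the stated power above 90% reproduces. At 30 per arm it is 99.98%.

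**Surgery rate.** Analysed: 75%. As randomized, with never-implanted subjects as failures: 0.75(30 − k)/30. Overstatement: 0.75k/30. If they responded at the 10% control rate instead: 0.65k/30.

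| k | As-randomized rate | Overstatement, as failures | Overstatement, at 10% |
|---|---|---|---|
| 1 | 72.5% | 2.5 points | 2.2 points |
| 2 | 70.0% | 5.0 points | 4.3 points |
| 3 | 67.5% | 7.5 points | 6.5 points |

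**Offset from controls.** Take 3 responders among 30 controls (10.0%), and let the dropped controls be non-responders. Dropping 1, 2 or 3 gives 3/29 = 10.3%, 3/28 = 10.7% or 3/27 = 11.1%, that is 0.3, 0.7 or 1.1 points against surgery.

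**Net effect on the difference, never-implanted as failures.**
- One lost per arm: 75.0 − 10.3 = 64.7 analysed, against 72.5 − 10.0 = 62.5; overstated by 2.2 points.
- Three lost per arm: 75.0 − 11.1 = 63.9 analysed, against 67.5 − 10.0 = 57.5; overstated by 6.4 points.

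**Effect on the test.** Take k fixed failures, the other 30 − k surgery eyes binomial at 0.75, and 30 controls at 0.10. Exact power is 99.85% at k = 3, 99.2% at k = 6, 94.4% at k = 10, 91.5% at k = 11 and 87.6% at k = 12. Against 3/30 in control, 11/30 surgery responders already give two-sided p = 0.03.

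**The tipping-point criterion.** The plan does not say which quantity's lower limit is compared with 75%.
- Read as the surgery-arm rate, exact lower 97.5% limits are 54.1% at 22/30, 57.7% at 23/30, 73.5% at 27/30 and 77.9% at 28/30. So 28/30 is needed, which has about a 1% chance at a true rate of 75% with complete data.
- Read as the difference, the planned value is only 75 − 10 = 65 points, already below 75.

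Example: 20 of 27 implanted eyes respond and 3 subjects are never implanted; 3 of 27 controls respond and 3 have no data. If all six were imputed, the 4 × 4 = 16 combinations give surgery-arm lower limits of 47.2% to 57.7%. All would be flagged, although the Fisher p-value never exceeds 0.0006.

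**The case against.** The strongest reply is that Section 11.4 is itself a prespecified rule. Section 11.0 says the sub-study evaluates the implant procedure, so restricting to implanted eyes can be seen as a choice. This stands in part. A reader might infer that the plan has no rule at all, and that is too strong: it has one, but it conflicts with the randomized-group definitions in 11.2 and 11.8. What is missing is an as-randomized rule. The implanted-only rate need not be wrong as a description of implanted eyes.

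The second reply is that the effect is conditional and small. The documents give no count of never-implanted subjects, Surgical Withdrawals are to be accounted for, and Objective #2 succeeds on the Fisher test alone, for which the sample is ample. All of this stands and limits how serious the point is.

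Third, some losses run the other way or are already handled. Controls without data are dropped to surgery's disadvantage, explanted eyes remain as failures, and partly implanted eyes remain in. This is correct, but the control offset is much smaller than the overstatement.

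Fourth, Discontinued has an open-ended reason, so the tipping-point analysis might reach eyes that were prepared but not implanted. That is unclear. The separate listing of Surgical Withdrawal argues against stretching it to those subjects, and the 75% limit would still not compare surgery with control. The unsuitable limit is a separate defect that exists even with k = 0. It matters here only because it stops the sensitivity analysis from serving as a safeguard.

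**Conclusion.** The point holds as an inconsistency that should be corrected. Followed as written, the plan leaves never-implanted surgery subjects out of a comparison it defines on the randomized groups, and its sensitivity analysis does not show what they would change.

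Under the stated assumptions the surgery rate is overstated by 2.5 points for each such subject out of 30. Net of equal control losses, the difference is overstated by about 2 points at one lost per arm and about 6 at three. With no such subjects the effect is zero.

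A reader might go further and infer that the Objective #2 conclusion is in doubt. The plan's figures do not support that: with these subjects counted as failures, power stays above 90% until 12 of 30 are never implanted. What is affected is the estimate and the usefulness of the sensitivity analysis. Figure 9 is not shown and parts of the document are redacted, so this rests on the readable text.

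**What to change.** - Make all randomized subjects, by assigned arm, the Objective #2 primary analysis set, and align Sections 11.2, 11.4 and 11.6.
- Count surgery-arm subjects never implanted as non-responders, including eyes prepared but given no segment.
- For symmetry, count controls with no month 3 to 6 data as non-responders; Section 11.6 itself expects failure in them. If only the surgery arm were changed, three lost per arm would give 67.5 − 11.1 = 56.4 points, below the as-randomized 57.5.
- Keep the Section 11.6 borrowing rules for eyes that have data, and the explant rule. Report the implanted-only result as a sensitivity analysis.
- Extend the tipping-point analysis to every randomized eye in either arm without usable 6-month data: surgical withdrawals, implanted eyes lost to follow-up, and controls with no month 3 to 6 data. Judge it by the Section 11.8 Fisher comparison instead of the 75% limit.

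The cost is SAP wording and one or two extra tables, with no new visits or data. The reported surgery rate may be slightly lower and will describe assignment to surgery; the implanted-only analysis still shows the result of completed implantation.
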